[Part 2 of 2 of the document. The other parts are not shown.]

CCI samples will be collected from all patients to assess exploratory **CCI**. These samples will be collected as per the timepoints in Section 10.2.

Table 20 **CCI** Sampling Schedule (All Patients)

Day	Timing for CCI	Window
Screening	At any screening visit	Not applicable
Cycle 1, Weeks 1-3	Predose	Within 2 hours before the start of the infusion
	4 hours after the start of the infusion	± 30 minutes
	7 hours after the start of the infusion	± 1 hour
	24 hours after the start of the infusion	± 1 hour
	48 hours after the start of the infusion	-2/+12 hours
	96 hours after the start of the infusion	-2/+12 hours
	Predose the following infusion	Within 4 hours before the start of the infusion
Any visit from Cycle 1, Week 4 onwards	Each timepoint where chemistry panel testing is performed	N/A
	Same schedule as Cycle 1, Weeks 1-3	N/A

For all patients, **CCI** samples will be collected during Cycle 1, Weeks 1 to 3. In addition, if a patient has **CCI**

CCI samples should also be taken at 48 hours and 96 hours after the start of the infusion (-2/+12 hours), predose the following infusion (within 4 hours), and whenever chemistry panel testing is being performed, until resolution of the event.

CCI

CCI sampling should be performed using the timepoints at least at 48 hours and 96 hours after the start of the infusion (-2/+12 hours) as outlined in **Table 20** (excluding Screening sample).

17.9 Exploratory Whole Blood Analyses Samples

By consenting to participate in the study, the patient consents to participate in the mandatory research components of the study.

Samples for **CCI** [REDACTED] are required and will be collected from all patients.

Mandatory whole blood samples will be collected from all patients as per the schedule in [Table 21](#) and the sections below.

Table 21 Exploratory Whole Blood Analyses Samples (All Patients) - MODULE 1

Samples	Screening	Timepoints ^a																		Tumour Assessment Scans ^b	EOT ^c
		C1 Week 1				C1 Week 2				C1 Week 3				C1 W5	C2 D1	C2 D15	C3 D1	C5 D1	C6 D1	C7 D1	
		Pre	Post (2h)	24h	Pre	Post (2h)	24h	Pre	Post (2h)	24h	Pre	Pre	Pre	Pre	Pre	Pre	Pre	Pre	Pre		
CCI [REDACTED]	X	X							X			X	X	X	X	X	X	X	X	X	X
CCI [REDACTED]	X	X							X			X	X	X	X	X	X	X	X	X	X
CCI [REDACTED]	X	X							X		X ^B		X	X	X	X		X	X	X	X
CCI [REDACTED]	X	X							X				X	X						X	X
CCI [REDACTED]	X ^B	X ^B											X ^B		X ^B	X ^B		X ^B	X ^B	X ^B	X ^B
CCI [REDACTED]	X	X	X	X	X	X	X	X	X	X	X		X		X	X		X	X	X	X

^a Timepoints include the following windows: pre-dose = within 2 h prior to dosing; post-dose = 2 h (\pm 15 min) after start of infusion, and 24h = 24 h(\pm 2 h) after start of infusion.

^b Every scheduled or unscheduled tumour assessment scan (if on the day of infusion, collect pre-infusion)

^c Disease progression/End of Treatment; if not collected at End of Treatment, the sample should be collected at the 30d Safety Follow-Up visit

d CCI [REDACTED]

e CCI [REDACTED]

f CCI [REDACTED]

g CCI [REDACTED]

h CCI [REDACTED]

Note: For all analytes, if a sample is not taken at End of Treatment, a sample should be obtained at the 30-day SFU.

Abbreviations: ^B = Part B only; C1W5 = Cycle 1 Week 5; C2D1 = Cycle 2, Day 1; EOT= end of treatment; CCI [REDACTED]

CCI [REDACTED] post = post-dose; pre = pre-dose; 24h = 24 h after infusion; SFU = safety follow-up.

17.9.1 Whole Blood for Exploratory [REDACTED] (Part A and B)

Mandatory whole blood samples to enable exploratory [REDACTED] analysis will be collected as specified below. Note: Collection time begins with the start of the infusion.

- Screening
- Cycle 1, Weeks 1, 3, and 5:
 - Predose (within 2 hours prior to dosing)
- Cycle 2, Days 1 and 15:
 - Predose (within 2 hours prior to dosing)
- Day 1 of Cycles 3, 5, 6, and 7:
 - Predose (within 2 hours prior to dosing)
- Every scheduled or unscheduled tumour assessment scan (if on day of infusion, collect pre-infusion)
- Disease progression/End of treatment - if a sample is not taken at End of Treatment, a sample should be obtained at the 30-day SFU.

17.9.2 Whole Blood for [REDACTED] Analysis (Part A and B)

Mandatory whole blood samples [REDACTED]

[REDACTED] Note: Collection time begins with the start of the infusion.

- Screening
- Cycle 1, Weeks 1, 3, and 5:
 - Predose (within 2 hours prior to dosing)
- Cycle 2, Days 1 and 15:
 - Predose (within 2 hours prior to dosing)
- Day 1 of Cycles 3, 5, 6, and 7:
 - Predose (within 2 hours prior to dosing)
- Every scheduled or unscheduled tumour assessment scan (if on day of infusion, collect pre- infusion)
- Disease progression/End of treatment - if a sample is not taken at End of Treatment, a sample should be obtained at the 30-day SFU.

17.9.3 Whole Blood Samples for CCI

Mandatory whole blood samples will be collected from all patients at the timepoints indicated below. CCI

Note:

Collection time begins with the start of the infusion.

Part A

- Screening
- Cycle 1, Weeks 1 and 3:
 - Predose (within 2 hours prior to dosing)
- Cycle 2, Days 1 and 15:
 - Predose (within 2 hours prior to dosing)
- Day 1 of Cycles 3, 5, and 7:
 - Predose (within 2 hours prior to dosing)
- Every scheduled or unscheduled tumour assessment scan (if on day of infusion, collect pre-infusion)
- Disease progression/End of treatment - if a sample is not taken at End of Treatment, a sample should be obtained at the 30-day SFU.

Part B

- Screening
- Cycle 1, Week 1:
 - Predose (within 2 hours prior to dosing)
- Cycle 1, Week 3:
 - Predose (within 2 hours prior to dosing)
 - 24 hours (\pm 2 hours) after the start of the infusion (and prior to acalabrutinib dosing)
- Cycle 2, Days 1 and 15:
 - Predose (within 2 hours prior to dosing)
- Day 1 of Cycles 3, 5, and 7
 - Predose (within 2 hours prior to dosing)
- Every scheduled or unscheduled tumour assessment scan (if on day of infusion, collect pre-infusion)

- Disease progression/End of treatment - if a sample is not taken at End of Treatment, a sample should be obtained at the 30-day SFU.

17.9.4 Whole Blood Samples for CCI (Part A and B)

Mandatory whole blood samples will be collected from all patients at the timepoints indicated below. CCI

time begins with the start of the infusion.

Note: Collection

Part A

- Screening
- Cycle 1, Week 1:
 - Predose (within 2 hours prior to dosing)
- Cycle 1, Week 3
 - Predose (within 2 hours prior to dosing)
- Cycle 2, Days 1 and 15:
 - Predose (within 2 hours prior to dosing)
- Every scheduled or unscheduled tumour assessment scan (if on day of infusion, collect pre-infusion)
- Disease progression/End of treatment - if a sample is not taken at End of Treatment, a sample should be obtained at the 30-day SFU.

Part B

- Screening
- Cycle 1, Week 1:
 - Predose (within 2 hours prior to dosing)
- Cycle 1, Week 3
 - Predose (within 2 hours prior to dosing)
- Cycle 2, Days 1 and 15
 - Predose (within 2 hours prior to dosing)
- Every scheduled or unscheduled tumour assessment scan (if on day of infusion, collect pre-infusion)
- Disease progression/End of treatment - if a sample is not taken at End of Treatment, a sample should be obtained at the 30-day SFU.

17.9.5 Whole Blood for **CCI** Exploratory Analysis (Part B Only)

Mandatory whole blood samples will be collected from all patients in **CCI** at the timepoints indicated below to analyse **CCI**

Note:

Collection time begins with the start of the infusion.

- Screening
- Cycle 1, Week 1:
 - Predose (within 2 hours prior to dosing)
- Day 1 of Cycles 2, 3, 5, and 7
 - Predose (within 2 hours prior to dosing)
- Every scheduled or unscheduled tumour assessment scan (if on day of infusion, collect pre-infusion)
- Disease progression/End of treatment - if a sample is not taken at End of Treatment, a sample should be obtained at the 30-day SFU.

17.9.6 Exploratory Blood **CCI** Samples

Mandatory whole blood samples will be collected in **CCI** from all patients at the timepoints indicated below. **CCI**

Note: Collection time begins

with the start of the infusion (see Section 10.2).

Part A and Part B

- Screening
- Cycle 1, Weeks 1 through 3 (AZD4573 first and second ramp-up and target dose and target dose):
 - Predose (within 2 hours prior to dosing)
 - 2 hours (\pm 15 minutes) after the start of the infusion
 - 24 hours (\pm 2 hours) after the start of the infusion (and prior to acalabrutinib dosing)
- Day 1 of Cycles 2, 3, 5, and 7:
 - Predose (within 2 hours prior to dosing)
- Every scheduled or unscheduled tumour assessment scan (if on the day of infusion, collect pre-infusion)

- Disease progression/End of treatment - if a sample is not taken at End of Treatment, a sample should be obtained at the 30-day SFU.

Further details on sample processing, handling, and shipment are provided in the Laboratory Manual.

17.10 CCI

CCI

17.10.1 Collection of Archival Tumour Samples

All patients in Part A (dose setting) must consent to and provide a sample of their archival tumour obtained within 24 months before the first dose of treatment. The archival tumour biopsy sample formalin-fixed paraffin embedded (FFPE) tumour block should be provided with sufficient material to produce 20 slides, or where an archival tumour biopsy FFPE tumour block is unavailable, archival tumour biopsy FFPE unstained slides (20 unstained slides preferable, minimum 15 slides acceptable) must be provided. Archival tissues must have been obtained as a core biopsy and meet the specified criteria detailed in the Laboratory Manual. Associated pathology report(s) for archival tissue samples must be obtained at Screening for all patients enrolled into the study.

If archival material is unavailable or unsuitable for use, patients must consent to and undergo a tumour biopsy during the screening period. A new biopsy is strongly encouraged and preferred over an archival sample (see Section 17.10.2) as these samples will be used to confirm cell of origin status and to determine additional DLBCL subtyping. A patient will be enrolled based on a prior pathology report.

Further details on sample processing, handling and shipment are provided in the Laboratory Manual.

17.10.2 Collection of Tumour Biopsy Samples

Patients in Part A who are unable to provide archival tumour specimens obtained within 24 months before the first dose of treatment will be asked to undergo a tumour biopsy at Screening. A new biopsy is strongly encouraged and preferred over an archival sample.

All patients in Part B (Phase II cohort expansions) will be asked to provide a newly obtained tumour biopsy at Screening. This sample will be used to confirm cell of origin

status, determine additional DLBCL subtype, and evaluate potential patient selection biomarkers through methods such as, but not limited to, immunohistochemistry (eg, baseline expression of Bfl1), gene expression analysis, and DNA sequencing. A patient will not be enrolled into Part B if he/she is unable to provide a newly obtained or recent biopsy. A recent biopsy that was taken as part of SoC prior to screening consent for this study is acceptable if no treatment was administered between the biopsy and the first dose of study treatment, and the biopsy was taken within 60 days prior to receiving the first dose.

All patients are also encouraged to consent to an additional optional tumour biopsy at disease progression. The optional disease progression sample may be taken at the 30-day SFU visit if not collected previously (see Section 17.10.5).

The tumour biopsy procedure will be performed by core needle, under radiological guidance, or surgically if the site of disease is superficial and palpable or visible (eg, palpable lymph node). Tumour biopsies should be preferentially obtained from tumour tissues that are safely accessible, as determined by the Investigator, and are not obtained from sites that require significant risk procedures. Patients will undergo 6 core image-guided needle biopsies. It is mandated that the core biopsy be removed directly from the tumour *in situ* and not cored from a surgically removed tumour. This is to ensure the best possible quality of the biopsy, as the blood/nutrient supply to the tumour is not disrupted prior to biopsy collection. Fine-needle aspirate specimens are not acceptable. Failure to obtain sufficient tumour sample after making best efforts to biopsy the tumour will not be considered a protocol deviation.

Sites should confirm the adequacy of tumour biopsy material at the time of the procedure. The exact time that the biopsy was taken should be clearly noted in the associated documentation. For mandatory and optional biopsy patients, the associated pathology report(s) for fresh tumour samples will be required at Screening and requested on treatment for all patients enrolled into the study.

Further details on sample processing, handling, and shipment are provided in the Laboratory Manual.

17.10.3 Collection of Bone Marrow

For all patients, when bone marrow biopsy and aspirate samples are collected for local standard disease profiling (refer to Section 17.4.3 for timepoints), **CC1**

CC1

Instructions on sample collection, labelling, processing, storage, and shipping will be provided in the laboratory manual.

17.10.4 Other Study Related CCI Research

17.10.4.1 CCI Sample for CCI Isolation

CCI

The sample should be collected from patients before receiving study treatment (Cycle 1, Week 1: Predose).

Details on sample processing, handling, and shipment are provided in the Laboratory Manual.

17.10.5 Collection of Optional CCI Samples

Collection of optional samples for CCI research is also part of this study as specified in the SoA (Section 10.2) and is subject to agreement to optional consent.

17.10.5.1 Optional Tumour Biopsy at Disease Progression

For patients who consent to the optional tumour biopsy, a biopsy will be taken at disease progression. The disease progression sample may be taken at the SFU visit if not collected previously.

Details on sample processing, handling, shipment, and storage are provided in the Laboratory Manual.

17.11 Optional Genomics Initiative Sample

Collection of optional saliva samples for genomics initiative research is also part of this study as specified in the SoA (Section 10.2) and is subject to agreement in the ICF addendum.

A saliva sample for DNA isolation will be collected from patients who have consented to participate in the genetic analysis component of the study. Participation is optional.

Patients who do not wish to participate in the genetic research may still participate in the study.

The saliva sample for exploratory genetic research will be obtained from the patients before the first dose of IP. If for any reason the sample is not taken before dosing it may be taken at any visit until the last study visit. Only one sample should be collected per patient for genetics during the study. Samples will be collected, labelled, stored, and shipped as detailed in the Laboratory Manual.

Please refer to [Appendix D](#) for information regarding the Genomics Initiative genetic sample. Details on processes for collection and shipment and destruction of these samples can be found either in the appendices or in the Laboratory Manual.

For storage and destruction of genetic samples, please refer to [Appendix D](#).

17.12 Medical Resource Utilisation and Health Economics

Health Economics/Medical Resource Utilisation and Health Economics parameters are not evaluated in this study.

17.13 Important Medical Procedures to be Followed by the Investigator

17.13.1 Medical Emergencies and Contacts

The principal Investigator(s) is responsible for ensuring that procedures and expertise are available to handle medical emergencies during the study. **A medical emergency usually constitutes an SAE and is to be reported as such, please refer to Section 8.2.10.**

In the case of a medical emergency the Investigator may contact the Medical Monitor. If the Medical Monitor is not available, contact the Medical Scientist.

18 STATISTICAL CONSIDERATIONS – MODULE 1

18.1 Statistical Hypotheses

No hypotheses are planned to be tested.

18.2 Sample Size Determination

Depending on dose escalation/de-escalation and enrolment in the expansion groups, up to a maximum of 105 evaluable patients will be treated with AZD4573 + acalabrutinib in this module.

The primary objective of Part A (dose setting) will be to identify the MTD and/or RP2D. In Part A, 3 to 9 evaluable patients may be treated in each of up to 3 dose levels using an mTPI-2 design permitting up to a maximum of 24 DLT-evaluable patients for dose setting (ie, a maximum of 9 evaluable patients at each of two dose levels and 6 evaluable patients at the third dose level). In addition, any safe dose level may be backfilled to include up to approximately 21 evaluable patients to collect additional tolerability and exploratory data. The maximum number of evaluable patients in Part A is therefore 63. This limits the number of patients exposed consistent with the expected safety profiles of the study drugs, but includes sufficient patients to explore safety of the combination treatment, PK, and effects on pharmacodynamic biomarkers, and to collect preliminary efficacy data.

In Part B (expansion), separate RP2D expansion cohorts will be opened for GCB and non-GCB DLBCL subtypes. For primary analyses, approximately 21 RP2D treated response evaluable patients of GCB subtype and approximately 21 RP2D-treated response-evaluable patients of non-GCB subtype will be incorporated, including patients from Part A and Part B. The total number of evaluable patients treated in Part B will be up to approximately 42. This sample size is large enough to evaluate further the safety and pharmacokinetics/pharmacodynamics (PKPD) of the chosen dose/schedule for AZD4573 + acalabrutinib from Part A and gives a reasonable chance of detecting an efficacy signal.

Historical response rates in r/r DLBCL are in the region of 30% to 60%, with some evidence that response rates are higher for the non-GCB subtype ([Hernandez-Ilizaliturri et al 2011](#), [Morschhauser et al 2014](#), [Van den Neste et al 2016](#), [Van den Neste et al 2017](#), [Wang et al 2018](#), [Wang et al 2020](#), [Wilson et al 2015](#), [Witzig et al 2011](#)). The following examples give an indication of the level of precision that will be achieved in this study:

- CCI

- CCI

- CCI

In addition to ORR, the criteria for success will take into account the observed safety and tolerability data, and the other efficacy endpoints, in particular the DoR.

The data cut-off for the primary analysis for each expansion subgroup will occur approximately 6 months following last patient first dose in the expansion subgroup or when 75% of patients have progressed or died in the cohort, whichever occurs first.

Treatment with AZD4573 and acalabrutinib, in Part A and Part B, may be continued until disease progression or an unacceptable drug-related toxicity occurs as defined in the protocol, or the patient withdraws or is withdrawn from the study for other reasons.

Patients who discontinue both study drugs before documented disease progression will be followed according to SoC until documented disease progression or the start of new anti-cancer therapy. All patients will be followed for survival until death, loss to follow-up, AstraZeneca closes study or withdrawal of consent, whichever occurs first.

18.3 Populations for Analyses

The analysis of data will be based on different subsets according to the purpose of the analysis.

Analysis sets are presented in [Table 22](#).

Table 22 Analysis Sets

Analysis Set	Definition
Enrolled	All participants who sign the ICF
Safety	All patients who received any amount of AZD4573 and/or acalabrutinib.
DLT-evaluable	
Patients that have received AZD4573 in combination with acalabrutinib and either:
 
• Have received at least 3 doses of AZD4573 at the designated target dose level, have received at least 75% of acalabrutinib doses, and have completed the SFU through the DLT-assessment period. 
Or
 
• Have experienced a DLT

Analysis Set	Definition
Pharmacokinetics	All dosed patients with reportable plasma concentrations and no important adverse events or protocol deviations that may impact PK.
Response evaluable	Patients dosed with AZD4573 or acalabrutinib with a baseline tumour assessment.
Interim response evaluable	Participants dosed with AZD4573 or acalabrutinib, or both AZD4573 and acalabrutinib with baseline tumour assessment and have their first post-baseline disease assessment performed, or have discontinued study treatment for any reasons before their first post-baseline disease assessment
FAS/ITT	All participants who received any amount of study intervention

Abbreviations: DLT = dose-limiting toxicity; ICF = informed consent form; FAS=Full analysis set; ITT = intent-to-treat; PK = pharmacokinetics.

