18.4.5 Efficacy

Tumour response data will be listed and summarised by dose level/cohort, if appropriate, using the standard response criteria as defined in Section [17.4](#).

For GCB and non-GCB RP2D expansion cohorts, the primary endpoint is ORR; other efficacy endpoints are secondary. For Part A participants who are not included in the GCB and non-GCB RP2D expansion cohorts, all efficacy endpoints are exploratory.

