18.4.5.1 Objective Response Rate and Proportion of Participants with Complete Response

Objective Response (OR) is defined as a best overall response of CR or PR that occurs prior to the initiation of subsequent anti-cancer treatment and prior to progression, or last evaluable assessment in the absence of progression. Objective Response Rate (ORR) is defined as the percentage of subjects with objective response ([Cheson et al 2014](#)). ORR and complete response rate (CRR) will be presented with corresponding 80% and 95% two-sided CIs.

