18.5 Interim Analyses

No interim analyses are planned for the study due to the decision to permanently halt enrolment.

18.6 Safety Review Committee – Module 1

An SRC, which includes the principal investigators, is tasked with the review of the available safety data (AEs and available pharmacokinetics/pharmacodynamics [PKPD] data) for AZD4573 in combination with acalabrutinib prior to the SRC making

recommendations on opening next cohorts or changing the dose schedule. All decisions are and will be documented in writing in the form of meeting minutes.

Please refer to Appendix [A 5](#) and the SRC Charter for further information on the SRC.

In Part A, once all participants in a given dose setting cohort have had the opportunity to become DLT-evaluable, the SRC will review and assess all available safety data, together with available PK data, to make a decision on the dose for the subsequent combination therapy cohort of participants. At least 3 evaluable participants are required before a dose-escalation decision can be made. Any dose interruptions and reductions will be taken into account.

The decision (guided by mTPI-2) may be to:

- 1 Proceed with dose escalation for the next cohort, up to a maximum of 9 evaluable participants per dose level.
- 2 Treat the next cohort at the same level, up to a maximum of 9 evaluable participants at any one dose level.
- 3 De-escalate the dose for the next cohort, up to a maximum of 9 evaluable participants at the lower dose level.
- 4 Stop the dose-escalation part of the study.
- 5 Evaluate alternative/intermittent dose schedules or change dosing to weight-based or body surface-area based dosing.

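### Module 1 primary ORR: the 75%-progressed-or-died cut-off has no minimum follow-up, so dosed patients not yet scanned can enter the denominator and pull ORR down

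*Protocol*

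**What the plan says.** Protocol Section 18.4.5 sets the endpoint: "For GCB and non-GCB RP2D expansion cohorts, the primary endpoint is ORR". Section 18.2 sets the analysis population: "For primary analyses, approximately 21 RP2D treated response evaluable patients of GCB subtype", with the same number for the non-GCB subtype. Table 22 in Section 18.3 defines response evaluable as "Patients dosed with AZD4573 or acalabrutinib with a baseline tumour assessment". Section 18.4.5.1 adds only that "Objective Response Rate (ORR) is defined as the percentage of subjects with objective response" and does not name the set.

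The cut-off for each expansion subgroup is in Section 18.2 and has two limbs. One is a fixed time, about half a year after the last patient in the subgroup starts treatment. The other is driven by events: "or when 75% of patients have progressed or died in the cohort, whichever occurs first".

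Table 22 also holds an interim response-evaluable set, whose members must "have their first post-baseline disease assessment performed, or have discontinued study treatment for any reasons before their first post-baseline disease assessment". Nothing in the part of the protocol at hand ties that set to the primary ORR, and Section 18.5 states: "No interim analyses are planned for the study due to the decision to permanently halt enrolment".

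**The concern.** A response can be recorded only from the first post-baseline scan onward. Under the 6-month limb, every patient still in follow-up has passed a first scan by the cut-off, so a denominator of dosed patients with a baseline assessment does no harm. The 75% limb is different. Early entrants can supply the events while the last entrants are still waiting for their first scan. Those late patients are in the denominator and cannot be in the numerator.

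ORR is the primary efficacy endpoint in small cohorts and is one of the stated criteria for success in Section 18.2. Faster progression among early patients brings the cut-off forward and so raises the number not yet assessed. Patients who die or progress before a scan are not the issue, because they are properly non-responders.

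**Working it through.** **1. The plan's own figures.** Section 18.2: 9 + 9 + 6 = 24 DLT-evaluable patients; 3 × 21 = 63 in Part A; 2 × 21 = 42 in Part B; 63 + 42 = 105. These reproduce. The ORR precision examples are redacted, and Section 18.1 plans no hypothesis test, so there is no power figure to check.

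**2. Upper bound.** 0.75 × 21 = 15.75, so the 75% limb needs 16 events. At most 21 − 16 = 5 patients (24%) can be event-free and unscanned.

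**3. Dilution.** If u of 21 patients are unscanned and would respond at the same rate p as the others, the expected reported ORR is p × (21 − u)/21. At the bound, u = 5:
- 30% × 16/21 = 22.9%
- 45% × 16/21 = 34.3%
- 60% × 16/21 = 45.7%

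The 30% and 60% are the ends of the historical range in Section 18.2.

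**4. How often, and how much on average.** This needs inputs that the document does not give. Assumptions:
- 21 patients, uniform accrual and exponential PFS with a median of 2, 3 or 4 months. Appendix A 11 gives a median OS of about 6 months for the Module 1 DLBCL population, and median PFS cannot exceed that.
- First scan at 8 weeks, from the Module 2 schedule (Table 37). The Module 1 schedule is not in the part at hand.
- 75% of events are seen at the next scan and 25% at once. The cut-off is the earlier of the 16th event and 6 months after last first dose.
- Only patients already dosed are counted, because Table 22 requires dosing.

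Results for 12-month accrual (ranges span repeat simulations):

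| Median PFS | At least one dosed patient unscanned | Mean share of dosed patients unscanned | True 40% reads on average |
|---|---|---|---|
| 2 months | 71–75% of cohorts | about 7% | 0.40 × 0.93 ≈ 37% |
| 3 months | 29–31% | about 2% | 0.40 × 0.98 ≈ 39% |
| 4 months | about 10% | about 0.7% | 0.40 × 0.993 ≈ 39.7% |

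The 75% limb comes first in 80–100% of these cohorts. The chance of at least one unscanned dosed patient depends strongly on accrual. For median PFS of 2, 3 and 4 months it is about 25%, 3% and 0% with 6-month accrual, and about 92%, 65% and 34% with 18-month accrual.

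**5. Wider range.** A second model let responders progress later than non-responders and let 20% of responses appear only at the second scan. It used accrual of 9 to 30 months, a first scan at 6 to 9 weeks, and median non-responder PFS / DoR from 1.5/3 to 3/9 months. The total bias was 0 to about −7 percentage points, of which unscanned patients account for 0 to about 5. The rest comes from patients scanned once who had not yet reached the second scan.

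**6. Candidate repairs in the same model.**
- Requiring the opportunity for two scheduled scans, with the denominator unchanged, left no bias beyond simulation error.
- Using the interim set as the denominator left up to about −2 points.

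**The case against.** The strongest objection is that enrolment is permanently halted (Section 18.5). The mechanism needs late entrants, and the simulations assume accrual that may never have taken that form. This stands. The cohort is now fixed, and the document does not say whether any dosed patient could be unscanned at the cut-off. Section 18.2 nevertheless still states the cut-off rule.

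Second, the size is modest. For 9 responders in 21 the exact 95% CI runs from 22% to 66%. No hypothesis is tested, no ORR threshold appears in the readable text, and a downward shift is conservative for an efficacy signal. This also stands and keeps the severity low. A wide interval does not remove a one-directional bias, however.

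Third, the SAP may specify how patients without a post-baseline scan are handled. That is possible, but the denominator and the cut-off rule are both fixed in the protocol, and it is their combination that matters.

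A reader might infer that the Module 1 ORR is biased down whatever happens. The documents do not support that: the bias arises only if the 75% limb is met first and a dosed patient has not yet been scanned. A reader might also infer that the protocol declares unscanned patients to be non-responders. No section at hand says so; it follows from the denominator. Nor is the dosed-plus-baseline set itself an error, since it is a defensible, non-selective choice.

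**Conclusion.** The point holds in conditional form. Read literally, Sections 18.2 and 18.3 allow dosed patients who have not reached their first scan to count against ORR when the 75% limb sets the cut-off. The effect is capped at 5 of 21 patients. Its average size is about 0.3 to 3 percentage points on a true 40% under 12-month accrual and median PFS of 4 down to 2 months, and it is negligible with 6-month accrual and median PFS of 3 months or more. These sizes rest on assumed accrual, PFS and scan timing; only the cap follows from the protocol's own numbers, taking the 75% over all 21 patients. Whether any patient is affected in practice cannot be told from the document. Severity: minor, a cheap improvement.

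**What to change.** In Section 18.2, add to the 75% limb: *provided every response-evaluable patient in the cohort has had the opportunity for the first two scheduled post-baseline disease assessments or has discontinued*. Keep the 6-month limb as the outer limit. Keep the dosed-plus-baseline denominator and name it as the ORR analysis set in Section 18.4.5.1.

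Do not move the primary ORR to the interim response-evaluable set. Early discontinuers enter that set at once while patients still on treatment wait for a scan, so some downward bias remains.

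The cost is one clause and one named set. The cut-off may move later, to at most about 17 weeks after last first dose on the assumed schedule (the second scan in the Module 2 tables). That is inside the existing limit of about 6 months.
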